6.6.4.3. Other Secondary Efficacy Endpoints

6.6.4.3.1. Hospitalizations for All-Cause LRTI through the RSV Season

Efficacy and its 2-sided 95% CIs for nirsevimab in reducing the incidence of hospitalizations for all-cause LRTI through the RSV season (overall and in each country) as compared to the no intervention will be calculated using the exact method as described in the primary efficacy analysis.

If a participant receives Beyfortus as part of a routine immunization, any events occurring after Beyfortus immunization will not be considered and the end date will be the date of injection of Beyfortus.

6.6.4.3.2. Efficacy Endpoints through Day 151 Post-Dosing/Randomization

Efficacy and its 2-sided 95% CIs for nirsevimab in reducing the following efficacy endpoints through Day 151 post-dosing/randomization as compared to the no intervention will be calculated using the exact method as described in the primary efficacy analysis for the exploratory purpose:

- Incidence of RSV LRTI hospitalization through Day 151 post-dosing/randomization (overall and in each country)

- Incidence of Very severe RSV LRTI through Day 151 post-dosing/randomization (overall and in each country)
- Incidence of hospitalization for all-cause LRTI through Day 151 post-dosing/randomization (overall and in each country)

Analyses for the above efficacy endpoints through Day 151 post-dosing/randomization will be performed only at the time of First Year Analysis after all data are collected. Participants who do not have any RSV LRTI hospitalization / Very severe RSV LRTI/ All cause LRTI hospitalization will be censored at the Day 151 or last available date for no event of interest whichever is earlier.

For participants who completed the study (Germany, France, UK non reconsented) or are ongoing (UK reconsented) at the time of First Year Analysis, the end date will be Day 151 or the last available date with confirmation of no efficacy endpoints of interest, whichever is earlier.

For participants who discontinued from the study before Day 151, the end date for the efficacy follow-up will be the date of the last available date with confirmation of no efficacy endpoints of interest.

For participants who had no contact for safety events at all at Day 151, the end date will be the start date (date of randomization for participants randomized to no intervention / date of immunization for participants randomized to nirsevimab and treated / date of randomization for participants randomized to nirsevimab but not treated).

For participants who had no contact for safety events at all at the cut-off date for the Primary Analysis but reported safety events with confirmation of no efficacy endpoint afterwards, the end date will be Day 151 or last available date with confirmation of no efficacy endpoint, whichever is earlier.

Notes:

- If efficacy endpoint-related events occur after Day 151, they will not be considered and the end date will be Day 151.
- If a participant receives Beyfortus as part of a routine immunization, any efficacy endpoint-related events occurring after Beyfortus immunization will not be considered and the end date will be the date of injection of Beyfortus.

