3.1.4. Handling of Intercurrent Events to Reflect the Clinical Question of Interest

The following intercurrent events are anticipated during the study:

- Participant ends study early and withdraws consent from further data collection
- Participant ends study early without withdrawing consent from further data collection
- Participant who received Beyfortus (nirsevimab) as a routine medication during the study

The following table describes how intercurrent events will be collected and handled within the analysis.

Table 2 Handling of Intercurrent Events for the Primary Estimand

Intercurrent event	Data collection and analysis
Participant ends study early and withdraws consent from further data collection	Participants who withdraw consent from further data collection will be analyzed by while on treatment strategy: only data collected before the occurrence of the intercurrent event will be included in the analysis. Participants will be censored at the earliest of: (i) last available date with no confirmation of RSV LRTI hospitalization, (ii) end of the RSV season or (iii) data cut-off date for the Primary Analysis (see section 6.7.8)
Participant ends study early without withdrawing consent from further data collection	Participants who end study early without withdrawing consent from further data collection will be analyzed with a treatment policy strategy: if RSV LRTI hospitalization occurs after cut-off date or end of the RSV season whichever is earlier, it will not be considered. Participants will be censored at the earliest of (i) last available date with no confirmation of RSV LRTI hospitalization, (ii) end of the RSV season or (iii) data cut-off date for the Primary Analysis
Participant who received Beyfortus (nirsevimab) as a routine medication during the study	Participants who received Beyfortus will be analyzed by while on treatment strategy: only data collected before the occurrence of the intercurrent event will be included in the analysis. Participants will be censored at the earliest of: (i) last available date with no confirmation of RSV LRTI hospitalization, (ii) end of the RSV season or (iii) data cut-off date for the Primary Analysis or (iv) start date of Beyfortus

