6.6.4.3.4. Efficacy Endpoints through Day 181 Post-Dosing/ Randomization

Efficacy and its 2-sided 95% CIs for nirsevimab in reducing the following efficacy endpoints as compared to the no intervention will be calculated using the exact method as described in the primary efficacy analysis for the following exploratory endpoint:

- Incidence of RSV LRTI hospitalization through Day 181 post-dosing/randomization (overall and in each country).
- Incidence of hospitalizations for all cause LRTI through Day 181 post-dosing/randomization (overall and in each country).

Analyses for the above efficacy endpoints through Day 181 post-dosing/randomization will be performed only at the time of First Year Analysis after all data are collected. Participants who do not have RSV LRTI hospitalization / All cause LRTI hospitalization will be censored at the Day 181 or last available date for no event of interest whichever is earlier.

For participants who completed the study (Germany, France, UK non reconsented) or are ongoing (UK reconsented) at the time of First Year Analysis, the end date will be Day 181 or the last available date with confirmation of no efficacy endpoints of interest, whichever is earlier.

For participants who discontinued from the study before Day 181, the end date for the efficacy follow-up will be the date of the last available date with confirmation of no efficacy endpoints of interest.

For participants who had no contact for safety events at all at Day 181, the end date will be the start date (date of randomization for participants randomized to no intervention / date of immunization for participants randomized to nirsevimab and treated / date of randomization for participants randomized to nirsevimab but not treated).

For participants who had no contact for safety events at all at the cut-off date for the Primary Analysis but reported safety events with confirmation of no efficacy endpoint afterwards, the end date will be Day 181 or last available date with confirmation of no efficacy endpoint, whichever is earlier.

Notes:

- If efficacy endpoint-related events occur after Day 181, they will not be considered and the end date will be Day 181.
- If a participant receives Beyfortus as part of a routine immunization, any efficacy endpoint-related events occurring after Beyfortus immunization but before Day 181 will not be considered and the end date will be the date of injection of Beyfortus.

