6.6.4.3.5. LRTI Hospitalization from 181 Days Post-Dosing/ Randomization to 366 Days Post-Dosing/ Randomization

Incidence of RSV LRTI hospitalization from 181 days post-dosing/randomization to 366 days post-dosing/randomization (overall and in each country) will be summarized by the treatment group. Descriptive statistics will be provided.

Incidence of hospitalizations for all-cause LRTI from 181 days post-dosing/randomization to 366 days post-dosing/randomization will also be summarized by treatment group, overall and in each country. Descriptive statistics will be provided.

Above analyses will be performed only in participants without the studied event before Day 181. In addition, number and percentage of participants with above efficacy events before and after Day 181 will be provided.

For participants who completed the study (Germany, France, UK non re-consented) or are ongoing (UK re-consented) at the time of First Year Analysis, the end date will be Day 366 or the last available date with confirmation of no efficacy endpoints of interest, whichever is earlier.

For participants who discontinued from the study before Day 366, the end date for the efficacy follow-up will be the date of the last available date with confirmation of no efficacy endpoints of interest.

For participants who had no contact for safety events at all at Day 366, the end date will be the start date (date of randomization for participants randomized to no intervention / date of immunization for participants randomized to nirsevimab and treated / date of randomization for participants randomized to nirsevimab but not treated).

For participants who reported safety events with confirmation of no efficacy endpoint, the end date will be Day 366 or last available date with confirmation of no efficacy endpoint, whichever is earlier.

Notes:

- If efficacy endpoint occurs after Day 366, it will not be considered and then the end date will be Day 366.
- If a participant receives Beyfortus as part of a routine immunization, any efficacy endpoint-related events occurring after Beyfortus immunization but between Day 181 and Day 366 will not be considered and the end date will be the date of injection of Beyfortus.

6.6.4.3.6. Incidence of RSV LRTI Hospitalization and Incidence of all-cause LRTI Hospitalization in UK Reconsented Participants only from 366 Days Post-Dosing/Randomization to 731 Days Post-Dosing/Randomization

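### Beyfortus notes for several non-confirmatory endpoints set the end date to the injection date without an earliest-of condition, in conflict with the window caps

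*SAP*

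**What the plan says.** For the primary estimand, SAP Table 2 (3.1.4) censors a routine Beyfortus recipient at the earliest of four dates, ending with "or (iii) data cut-off date for the Primary Analysis or (iv) start date of Beyfortus". Tables 3 and 4, for the two key secondary estimands, carry the same list.

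The notes for other endpoints are worded differently.

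- **6.6.4.3.1, all-cause LRTI through the season:** "any events occurring after Beyfortus immunization will not be considered and the end date will be the date of injection of Beyfortus".
- **6.6.4.3.2, Day 151 endpoints:** "any efficacy endpoint-related events occurring after Beyfortus immunization will not be considered and the end date will be the date of injection of Beyfortus". The note in 6.6.9.1 (post-hoc all-cause hospitalization, including the end-of-2022 endpoint) has the same words.
- **6.6.4.3.7, wheeze through Day 731:** the same construction, again with no bound.
- **6.6.4.3.4, Day 181 endpoints:** the events dropped are those "occurring after Beyfortus immunization but before Day 181 will not be considered and the end date will be the date of injection of Beyfortus".
- **6.6.4.3.5, Day 181 to Day 366:** the events dropped are those after Beyfortus "but between Day 181 and Day 366 will not be considered and the end date will be the date of injection of Beyfortus".

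The notes in 6.6.4.3.6 and 6.6.9.2.1, and the other two wheeze periods, follow the pattern of the last two items. They bound the events that are dropped but still name the injection date as the end date.

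Caps are also stated. Section 6.6.4.3.2 says that participants without an event "will be censored at the Day 151 or last available date for no event of interest whichever is earlier", and adds: "If efficacy endpoint-related events occur after Day 151, they will not be considered and the end date will be Day 151". Section 6.6.9.1 has the equivalent for 31 December 2022. Section 5.2.1 caps season follow-up at the First Year Analysis at the end of the season or the last confirmed event-free date.

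**The concern.** Person-time is the denominator of both incidence rates. A rule that ends follow-up at an intercurrent event should only ever shorten it. As written, the unbounded notes can lengthen it: an infant dosed after the window is credited with time in which no event can count. On the most literal reading, an infant already admitted with the endpoint is credited with time after that event.

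The same sections also cap follow-up at the window end, so two instructions apply to one infant and nothing says which prevails. Two programmers working from this text could produce different person-time. If late routine doses are more common in one arm, the efficacy estimate moves as well.

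**Working it through.** The plan states no figure that depends on this rule, so there is nothing to reproduce. The check is a comparison of rules, followed by an illustration of size.

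**Can a dose after the window be in the data?** Protocol 6.8 asks sites to report any routine Beyfortus dose, without a time limit. Planned last enrolment is 28 February 2023 (Protocol 4.1), so the last Day 151 is 150 days later, 28 July 2023, and the last Day 366 is 28 February 2024. The Day 151 endpoints are analysed only at the First Year Analysis. The end-of-2022 endpoint is analysed only at the Second Year Analysis. Late doses can therefore be present for these endpoints. For wheeze through Day 731 there is almost no time left after the window, and the conflict there is mainly with the rule that ends follow-up at the second wheeze episode.

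**Which end date applies? (Day 151 endpoints, dose on Day 300)**

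| Infant | Other rule | Beyfortus note |
|---|---|---|
| No event | Day 151 or last event-free date, if earlier (6.6.4.3.2) | Day 300 |
| Event after Day 151 | Day 151 (6.6.4.3.2) | Day 300 |
| Admitted on Day 40 | Day 40, by reference to 6.6.1 | Day 300 |

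**Person-time per infant.** SAP 6.6.1 gives (end − start + 1)/30.4375.

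- Day 151: 151/30.4375 = 4.96 months. Day 300: 300/30.4375 = 9.86 months. Day 40: 40/30.4375 = 1.31 months.
- A dose between Day 152 and Day 366 gives 4.99 to 12.02 months in place of 4.96, at most 366/151 = 2.4 times too much.

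**Effect on efficacy under the literal reading.** Let fC and fN be the shares of the control and nirsevimab arms dosed on day B after the window, with other infants followed to Day 151. Then

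efficacy = 1 − (1 − VE) × [1 + fC(B − 151)/151] / [1 + fN(B − 151)/151].

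VE = 60% is the design value (Protocol 9.2). B, fC and fN are assumptions, because the documents give none of them. With B = 300, (B − 151)/151 = 149/151 = 0.987.

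| fC | fN | Computed efficacy |
|---|---|---|
| 1% | 0 | 1 − 0.4 × 1.0099 = 59.6% |
| 5% | 0 | 1 − 0.4 × 1.0493 = 58.0% |
| 10% | 0 | 1 − 0.4 × 1.0987 = 56.1% |
| 10% | 2% | 1 − 0.4 × 1.0987/1.0197 = 56.9% |
| 5% | 5% | 60.0% |
| 0 | 5% | 1 − 0.4/1.0493 = 61.9% |

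With fC = 10% and fN = 0, moving the dose day from 200 to 366 moves the result from 58.7% to 54.3%. In the equal-uptake row efficacy is unbiased, but each arm's rate is divided by 1.0493, so it is about 4.7% too low.

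**The case against.** The strongest reply is that the notes were meant to truncate follow-up at a dose given inside the window. The parallel notes in 6.6.4.3.4 to 6.6.4.3.6 limit the dropped events to the window. The caps in 5.2.1, 6.6.4.3.2 and 6.6.9.1 make no exception for Beyfortus recipients. That intent is plausible, and much of this reply stands. It does not settle the matter: the intent is not written in the unbounded notes, and where a bound exists it governs which events are dropped and not the end date.

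The reply is stronger for infants with an event. Protocol 9.4.2 ends their follow-up at admission, and SAP 6.6.1 does so when the cut-off precedes the season end. Section 6.6.9.2.1 puts admission first and applies its censoring rules only otherwise. The Day 40 example therefore arises only if the note is allowed to override 6.6.1.

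Three stronger conclusions might be inferred, and the documents do not support them.

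- *Everything outside the primary estimand is affected.* Tables 3 and 4 already use the earliest-of rule for both key secondary estimands.
- *The plan definitely lengthens person-time.* The caps are also in the text. What is established is an unresolved conflict.
- *Efficacy is biased downward because control families would take up Beyfortus more often.* No document gives uptake by arm, and more late doses in the nirsevimab arm would reverse the direction. Uptake may also be very low, since the SAP makes its Beyfortus tables conditional on at least 10 recipients. Ten controls out of 14,430 dosed on Day 300 would give 1 − 0.4 × (1 + 10/14,430 × 0.987) = 59.97%.

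**Conclusion.** The point holds as a conflict between written rules. In 6.6.4.3.1, 6.6.4.3.2, 6.6.9.1 and the Day 731 wheeze note, the end date for a Beyfortus recipient is the injection date, with no earliest-of condition and no restriction to doses inside the window. This contradicts the Day 151, 31 December 2022 and season-end caps, and no precedence is given.

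The consequence is limited. The affected analyses are descriptive secondary, exploratory or post hoc, and no confirmatory test is touched. If the notes are programmed literally, rates are understated in any arm with late doses, and efficacy shifts only if late uptake differs between arms, in a direction set by which arm has more. The percentages above illustrate sensitivity to assumed uptake and timing. They are not estimates of what happened in this trial.

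**What to change.** Use one rule in 6.6.4.3.1, 6.6.4.3.2, 6.6.4.3.4 to 6.6.4.3.7, 6.6.9.1 and 6.6.9.2.1: the end date is the earliest of (a) the qualifying event date, meaning hospital admission or, for recurrent wheeze, the second episode; (b) the end of the window; (c) the last date with confirmation of no event; and (d) the Beyfortus injection date. This follows the earliest-of approach of Tables 2 to 4. The event date has to be written out because those tables do not list it. Section 6.6.7.1 refers to 6.6.4.3.4 for its censoring rules and would inherit the change.

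The cost is a wording change and a check of the derivation program, with no new data. If outputs already exist, a count by arm of Beyfortus recipients whose end date falls after the window end or after their own event would show whether any result changes.

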6.6.4.3.3. Survival Analyses for RSV LRTI Hospitalization through Day 151 Post-Dosing/Randomization

Same Cox proportional hazard model as in section 6.6.3.2 will be performed with country (ie, France, Germany and United Kingdom) and age group at randomization (ie, age \leq 3.0 months, age $>$ 3.0 to \leq 6.0 months, age $>$ 6.0 months) as the covariates.

For the analysis by country, only age group at randomization will be used as covariates as described in section 6.6.6.2.2.

Kaplan-Meier Plots will be provided for RSV LRTI hospitalization through Day 151 post-dosing/randomization (overall and in each country). P-value from Log Rank test will be provided.

6.6.4.3.4. Efficacy Endpoints through Day 181 Post-Dosing/ Randomization

Efficacy and its 2-sided 95% CIs for nirsevimab in reducing the following efficacy endpoints as compared to the no intervention will be calculated using the exact method as described in the primary efficacy analysis for the following exploratory endpoint:

- Incidence of RSV LRTI hospitalization through Day 181 post-dosing/randomization (overall and in each country).
- Incidence of hospitalizations for all cause LRTI through Day 181 post-dosing/randomization (overall and in each country).

Analyses for the above efficacy endpoints through Day 181 post-dosing/randomization will be performed only at the time of First Year Analysis after all data are collected. Participants who do not have RSV LRTI hospitalization / All cause LRTI hospitalization will be censored at the Day 181 or last available date for no event of interest whichever is earlier.

For participants who completed the study (Germany, France, UK non reconsented) or are ongoing (UK reconsented) at the time of First Year Analysis, the end date will be Day 181 or the last available date with confirmation of no efficacy endpoints of interest, whichever is earlier.

For participants who discontinued from the study before Day 181, the end date for the efficacy follow-up will be the date of the last available date with confirmation of no efficacy endpoints of interest.

For participants who had no contact for safety events at all at Day 181, the end date will be the start date (date of randomization for participants randomized to no intervention / date of immunization for participants randomized to nirsevimab and treated / date of randomization for participants randomized to nirsevimab but not treated).

For participants who had no contact for safety events at all at the cut-off date for the Primary Analysis but reported safety events with confirmation of no efficacy endpoint afterwards, the end date will be Day 181 or last available date with confirmation of no efficacy endpoint, whichever is earlier.

Notes:

- If efficacy endpoint-related events occur after Day 181, they will not be considered and the end date will be Day 181.
- If a participant receives Beyfortus as part of a routine immunization, any efficacy endpoint-related events occurring after Beyfortus immunization but before Day 181 will not be considered and the end date will be the date of injection of Beyfortus.

6.6.4.3.5. LRTI Hospitalization from 181 Days Post-Dosing/ Randomization to 366 Days Post-Dosing/ Randomization

Incidence of RSV LRTI hospitalization from 181 days post-dosing/randomization to 366 days post-dosing/randomization (overall and in each country) will be summarized by the treatment group. Descriptive statistics will be provided.

Incidence of hospitalizations for all-cause LRTI from 181 days post-dosing/randomization to 366 days post-dosing/randomization will also be summarized by treatment group, overall and in each country. Descriptive statistics will be provided.

Above analyses will be performed only in participants without the studied event before Day 181. In addition, number and percentage of participants with above efficacy events before and after Day 181 will be provided.

For participants who completed the study (Germany, France, UK non re-consented) or are ongoing (UK re-consented) at the time of First Year Analysis, the end date will be Day 366 or the last available date with confirmation of no efficacy endpoints of interest, whichever is earlier.

For participants who discontinued from the study before Day 366, the end date for the efficacy follow-up will be the date of the last available date with confirmation of no efficacy endpoints of interest.

For participants who had no contact for safety events at all at Day 366, the end date will be the start date (date of randomization for participants randomized to no intervention / date of immunization for participants randomized to nirsevimab and treated / date of randomization for participants randomized to nirsevimab but not treated).

For participants who reported safety events with confirmation of no efficacy endpoint, the end date will be Day 366 or last available date with confirmation of no efficacy endpoint, whichever is earlier.

Notes:

- If efficacy endpoint occurs after Day 366, it will not be considered and then the end date will be Day 366.
- If a participant receives Beyfortus as part of a routine immunization, any efficacy endpoint-related events occurring after Beyfortus immunization but between Day 181 and Day 366 will not be considered and the end date will be the date of injection of Beyfortus.

6.6.4.3.6. Incidence of RSV LRTI Hospitalization and Incidence of all-cause LRTI Hospitalization in UK Reconsented Participants only from 366 Days Post-Dosing/Randomization to 731 Days Post-Dosing/Randomization

At the time of Second Year Analysis, incidence of RSV and all-cause LRTI hospitalization in UK reconsented participants only from 366 days post-dosing/randomization to 731 days post-dosing/randomization will be summarized by the treatment group. Descriptive statistics will be provided only.

Above analyses will be performed only in participants without the studied event before Day 366. In addition, number and percentage of participants with above events before and after Day 366 will be provided.

For UK reconsented participants who completed the study, the end date of the follow-up time will be the end of study date or the last available date with confirmation of no RSV/all-cause LRTI hospitalizations, whichever is earlier.

For UK reconsented participants who had contact for safety events after reconsented and discontinued from the study before Day 731, the end date of the follow-up time will be the last available date with confirmation of no RSV/all-cause LRTI hospitalizations.

For UK reconsented participants who had no contact for safety events at all after reconsenting, the end date of the follow-up time will be the consent date.

For UK reconsented participants who had no contact for safety events at all at the time of First Year Analysis but reported safety events with confirmation of no RSV/all-cause LRTI hospitalizations afterwards, the end date of the follow-up time will be the end of study date or last available date with confirmation of no RSV/all-cause LRTI hospitalizations, whichever is earlier.

Notes:

- If RSV/all-cause LRTI hospitalizations occur after Day 731, it will not be considered and then the end date will be Day 731.

- If a participant receives Beyfortus as part of a routine immunization, any RSV/all-cause LRTI hospitalization occurring after Beyfortus immunization but between Day 366 and Day 731 will not be considered and the end date will be the date of injection of Beyfortus.

